### **6.3.6. Second Primary Malignancies**

The second primary malignancies during the study will be summarized by cancer type and preferred term. A listing of subjects who reported second primary malignancies during the study will also be provided. This listing will include diagnosis, study day of diagnosis, recurrence of a prior existing malignancy (yes, no) and pathology diagnosis (biopsy, aspirate etc.) information whenever a second primary malignancy is observed. In addition, cumulative study drug exposure, the treatment for second primary malignancy and the outcome information will also be presented in the listing.

### **6.3.7. Adverse Events by Subgroups**

The subgroup analysis for the following TEAEs will be performed based on the subgroups specified in Section 2.10:

- Overview of TEAEs

- Summary of all TEAEs
- Grade 3 or 4 TEAEs
- Serious TEAEs

#### 6.4. Clinical Laboratory Tests

The evaluation of clinical laboratory tests will focus on the following selected laboratory analytes:

- Hematology Panel:
  - hemoglobin
  - white blood cell (WBC) count, absolute neutrophil count, and absolute lymphocyte count
  - platelet count
- Serum Chemistry Panel:
  - AST
  - ALT
  - total bilirubin
  - glucose
  - creatinine
  - sodium
  - alkaline phosphatase
  - uric acid
  - blood urea nitrogen (BUN) or urea
  - calcium and albumin-adjusted calcium
  - lactic acid dehydrogenase (LDH)
  - potassium

Descriptive statistics for values and changes from baseline at each scheduled visit for hematology and chemistry laboratory parameters will be provided. Line plot of mean with standard error for each laboratory analyte over time will be displayed by treatment group for hemoglobin, neutrophils, lymphocytes, platelets, WBC, AST, ALT, and creatinine.

In addition, the worst toxicity grade in hematology and chemistry during the treatment will be summarized by treatment group and toxicity grade. Shifts tables from baseline to the worst toxicity grade during treatment will be generated.

#### 6.5. Vital Signs and Physical Examination Findings

Descriptive statistics will be provided for values and changes from baseline over time for vital signs (pulse, temperature, systolic and diastolic blood pressure) at each scheduled visit. Similar analysis may be performed for weight at Day 1 of each treatment cycle.

Clinically significant physical examination findings occurred at post-baseline were collected as AEs, and therefore will not be summarized.

#### 6.6. Electrocardiogram

The ECG data will be collected at Screening, visits as clinically indicated during treatment, and End-of-Treatment visit.

The number and percentage of subjects with normal and abnormal either clinically significant or not clinically significant ECG results will be summarized for each treatment group.

A listing of subjects who experienced clinically significant abnormal ECGs in either baseline or post-baseline will be produced.

## 6.7. ECOG Performance Status

ECOG performance status, which evaluates the effect of the disease status on the activities of daily living, will be assessed at Screening, Day 1 of each treatment cycle and end-of-treatment visit. The shift summaries of ECOG performance status from baseline to each scheduled visit, including Day 1 of each treatment cycle and end-of-treatment visit, will be provided for each treatment group. The shift summary from baseline to the worst performance score during treatment will also be presented.

## 7. PHARMACOKINETICS/IMMUNOGENICITY/PHARMACODYNAMICS

Unless specified otherwise, descriptive statistics will be used to summarize pharmacokinetics and pharmacodynamics data. In addition, coefficient variation and geometric mean will be provided in the pharmacokinetic concentration summary.

### 7.1. Pharmacokinetics

All serum concentrations below the lowest quantifiable concentration or missing data will be labeled as such in the concentration data presentation. Concentrations below the lowest quantifiable concentration will be treated as zero in the summary statistics.

The pharmacokinetic parameters are defined as:

- Maximum  $C_{\text{trough}}$  - Serum pre-dose concentration of daratumumab on Cycle 3 Day 1
- $C_{\text{min}}$  - Minimum observed concentration
- $C_{\text{max}}$  - Maximum observed concentration

The Maximum  $C_{\text{trough}}$ ,  $C_{\text{min}}$ , and  $C_{\text{max}}$  will be determined based on the assigned collection timepoints. If there are sufficient data, population pharmacokinetic analysis of serum concentration-time data of daratumumab may be performed using nonlinear mixed effects modeling and may include data from other clinical studies. If performed, details will be provided in a population pharmacokinetic analysis plan and results of the analysis will be presented in a separate report.

#### 7.1.1. Maximum $C_{\text{trough}}$

For the co-primary endpoint maximum  $C_{\text{trough}}$ , which is defined as the concentration at pre-dose on Cycle 3 Day 1, the summary statistics such as the geometric mean, coefficient of variation, median, and range will be provided by treatment group. The ratio of the geometric means and the

corresponding 90% confidence interval utilizing logarithmic transformation of  $C_{\text{trough}}$  values will be provided. If the lower bound of the 90% CI for the ratio of the geometric means of maximum  $C_{\text{trough}}$  is  $\geq 80\%$  (non-inferiority margin of 20%), Dara SC will be considered non-inferior to Dara IV.

Box plot of maximum  $C_{\text{trough}}$  will be provided.

The analyses of maximum  $C_{\text{trough}}$  will be performed on the pharmacokinetics-evaluable analysis set.

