3.2. Study Design Rationale

Blinding, Control, Study Phase/Periods, Treatment Groups

This is a study of subjects with multiple myeloma who have received at least 3 prior lines of therapy including a PI and an IMiD, or whose disease is refractory to both a PI and an IMiD. The approved route of administration of daratumumab in this population is IV infusion. This study is designed to determine if the ORR and maximum C_{trough} for single-agent Dara-SC are non-inferior to the ORR and maximum C_{trough} , respectively, for single-agent Dara-IV. Therefore, important efficacy assessments will be performed symmetrically in the 2 treatment groups. Furthermore, local tolerability data will be collected from the subject and the investigator, as well as patient reported outcomes data related to the different routes of administration.

Randomization will be used to minimize bias in the assignment of subjects to treatment groups, to increase the likelihood that known and unknown subject attributes (eg, demographic and baseline characteristics) are evenly balanced across treatment groups, and to enhance the validity of statistical comparisons across treatment groups. To further minimize treatment imbalance across prognostic groups, subjects will be stratified based on body weight at baseline (≤ 65 kg, 66 kg to 85 kg, >85 kg), number of prior lines of therapy (≤ 4 prior lines versus >4 prior lines), and type of myeloma (IgG versus non-IgG).

Rationale for Co-primary Endpoints

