5. TREATMENT ALLOCATION AND BLINDING

Treatment Allocation

Central randomization will be implemented in this study. Subjects will be assigned randomly to 1 of 2 treatment groups based on a computer-generated randomization schedule prepared before the study by or under the supervision of the sponsor. The randomization will be balanced by using randomly permuted blocks and will be stratified by body weight at baseline (≤ 65 kg, 66 kg to 85 kg, >85 kg), number of prior lines of therapy (≤ 4 prior lines versus >4 prior lines), and type of myeloma (IgG versus non-IgG). The interactive web response system (IWRS) will assign a unique treatment code, which will dictate the treatment assignment and matching study drug kit

for the subject. The requestor must use his or her own user identification and personal identification number when contacting the IWRS, and will then give the relevant subject details to uniquely identify the subject.

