11.5. Pharmacokinetic Analyses

For the co-primary endpoint of maximum C_{trough} , the ratio of the geometric means and the corresponding 90% CI utilizing logarithmic transformation of maximum C_{trough} values will be provided. The 2 formulations of daratumumab will be considered similar if the lower bound of the 90% CI for the ratio of the geometric means of maximum C_{trough} is at least 80% (non-inferiority margin of 20%). Summary statistics such as the geometric mean, coefficient of variation, median, and range will be provided by treatment group.

All concentrations below the lowest quantifiable concentration or missing data will be labeled as such in the concentration database. Concentrations below the lowest quantifiable concentration will be treated as zero in the summary statistics. All subjects and samples excluded from the analysis will be clearly documented in the Clinical Study Report.

Descriptive statistics will be used to summarize daratumumab serum concentrations at each sampling time point and other pharmacokinetic parameters of daratumumab: C_{min} , and C_{max} . Additional pharmacokinetic parameters, when available, will also be summarized.

If sufficient data are available, then population pharmacokinetic analysis of serum concentration-time data of daratumumab may be performed using nonlinear mixed effects modeling and may include data from other studies. If the population pharmacokinetic analysis is conducted, details will be given in a population pharmacokinetic analysis plan and the results of the analysis will be presented in a separate report.

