## 1.6. Randomization and Blinding

Central randomization will be implemented in this study. Subjects will be assigned randomly to 1 of 2 treatment groups based on a computer-generated randomization schedule prepared before the study by or under the supervision of the sponsor. The randomization will be balanced by using randomly permuted blocks and will be stratified by body weight at baseline ( $\leq 65$  kg, 66 kg to 85 kg,  $> 85$  kg), number of prior lines of therapy ( $\leq 4$  prior lines versus  $> 4$  prior lines), and type of myeloma (IgG versus non-IgG). An interactive web response system (IWRS) will assign a unique treatment code, which will dictate the treatment assignment and matching study drug kit for the subject.

As this is an open-label study, blinding procedures are not applicable.

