### 5.2.3. Analysis Methods

The primary analysis of ORR will be performed on the ITT analysis set. The number and percentage of subjects in the following response categories will be tabulated by treatment group: sCR, CR, VGPR, PR, minimal response (MR), stable disease (SD), progressive disease (PD), and not evaluable (NE). The overall response (including sCR + CR + VGPR + PR), VGPR or better (sCR + CR + VGPR), and CR or better (sCR + CR) will also be summarized. For each of the above categories, two-sided 95% Clopper-Pearson exact confidence interval (CI) will also be presented by treatment group.

Farrington-Manning (FM) test will be used to test the overall response rate. The FM estimate of relative risk with its 2-sided 95% confidence interval and p-value will be reported. If the lower bound of the 95% CI is  $\geq 60\%$ , the non-inferiority of Dara SC relative to Dara IV will be concluded. If non-inferiority in ORR is established and the lower limit of the 95% CI of the relative risk is  $\geq 100\%$ , the superiority of Dara SC relative to Dara IV will be concluded.

A sensitivity analysis of ORR based on the per-protocol and response-evaluable analysis sets will be performed in a similar manner as described above.

A sensitivity analysis of ORR, in which disease response is based on investigator assessment according to the IMWG response criteria, will also be performed in a similar manner.

A supplementary analysis of ORR based on the first 480 randomized subjects in intent-to-treat analysis set will also be performed in a similar manner.

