#### **5.3.2.2. Analysis Methods**

The response rate of VGPR or better will be calculated for each treatment group on both ITT and response-evaluable analysis sets. The corresponding 95% Clopper-Pearson exact CI will be provided.

Stratified CMH test will be used to test the proportion of subjects who achieved a VGPR or better response. The CMH estimate of odds ratio and its 95% confidence interval and p-value will be reported. Stratification factors used in the analysis include body weight at baseline ( $\leq 65$  kg, 66 kg to 85 kg,  $>85$  kg), number of prior lines of therapy ( $\leq 4$  prior lines versus  $>4$  prior lines), and type of myeloma (IgG versus non-IgG).

A sensitivity analysis of response rate of VGPR or better, in which disease response is based on investigator assessment according to the IMWG response criteria, will be performed in a similar manner as described above.

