## **6.3. Adverse Events of Clinical Interest**

### **6.3.1. Infusion-related Reactions**

#### **6.3.1.1. Rate of Infusion-related Reactions**

For the major secondary endpoint of rate of IRRs, the proportion of subjects who have an IRR along with its 95% Clopper-Pearson exact CI will be calculated for each treatment group on the safety analysis set.

Stratified CMH test will be used to test the IRR rate. The CMH estimate of odds ratio and its 2-sided 95% confidence interval and p-value will be reported. Stratification factors used in the analysis include body weight at baseline ( $\leq 65$  kg, 66 kg to 85 kg,  $>85$  kg), number of prior lines of therapy ( $\leq 4$  prior lines versus  $>4$  prior lines), and type of myeloma (IgG versus non-IgG).

A subgroup analysis on rate of IRRs will be conducted for the subgroups of race and baseline weight defined in Section 2.10. A forest plot of the subgroup analysis on rate of IRRs will be generated.

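### No model is named for the co-primary Ctrough ratio; adjusting for the three randomisation factors costs almost nothing and tightens the 90% CI if they predict trough

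*SAP*

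**What the plan says.** **Randomisation.** Protocol 5 states: "The randomization will be balanced by using randomly permuted blocks and will be stratified by body weight at baseline", with number of prior lines and type of myeloma as the other two factors. SAP 1.6 repeats this. With 3, 2 and 2 levels there are 12 strata. Protocol 3.2 gives the reason: "To further minimize treatment imbalance across prognostic groups, subjects will be stratified based on body weight at baseline".

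**Maximum Ctrough.** Protocol 11.5 asks for "the ratio of the geometric means and the corresponding 90% CI utilizing logarithmic transformation of maximum" Ctrough, and SAP 7.1.1 likewise asks for the ratio with the "corresponding 90% confidence interval utilizing logarithmic transformation of" the trough values. Neither names a model, a covariate or a stratification factor.

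**Testing hierarchy (SAP 5.1.1).** All four endpoints use the three factors:
- IRR rate, SAP 6.3.1.1: "Stratified CMH test will be used to test the IRR rate".
- PFS, SAP 5.3.1.2: stratified log-rank test and stratified Cox model.
- VGPR or better, SAP 5.3.2.2: "Stratification factors used in the analysis include body weight at baseline", followed by the other two.
- OS, SAP 5.3.5.2: takes the PFS method by cross-reference.

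**ORR.** SAP 5.2.3 says "Farrington-Manning (FM) test will be used to test the overall response rate", without strata. Protocol 11.3 names the same test.

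**Analysis set.** Ctrough is analysed in the PK-evaluable set (SAP 2.6). It requires all eight weekly full doses within the dosing window and a Cycle 3 Day 1 pre-dose sample within eight hours before dosing. No expected size is given.

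**The concern.** The trial balances its arms on three factors, but the Ctrough analysis as written makes no use of that balance. When such factors predict the outcome, stratified randomisation reduces the true sampling variation of the treatment difference. The ordinary two-sample standard error still counts the between-stratum variance, so the 90% CI is wider than it needs to be.

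Both co-primary endpoints must pass (SAP 1.3). The PK-evaluable set can be smaller than the 480 used in the power statement. A tighter interval from the same data is therefore worth having if it is nearly free.

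A second, smaller matter is that the trial is open-label and the model behind a co-primary interval is not named. Naming it removes an analyst choice.

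**Working it through.** **Inputs from SAP 1.5 and Protocol 11.2:** 240 per arm, CV 0.6, true ratio 1, margin 0.80, one-sided alpha 0.05, stated power above 95%. **Assumed, because the documents give no value:** the share R² of log-Ctrough variance explained by the three factors (0 to 30%), and a smaller evaluable set of 150 per arm.

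**1. Reproduce the stated power.** SD on the log scale = sqrt(ln(1 + 0.6²)) = sqrt(0.307) = 0.5545. SE = 0.5545 × sqrt(2/240) = 0.0506. Distance to the margin = ln(1/0.80) = 0.2231. Power = Φ(0.2231/0.0506 − 1.645) = 99.7%, which agrees with the plan. The same formula gives 96.7% at 150 per arm and reaches 95% at 134 per arm.

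**2. Cost if the factors explain nothing.** Main effects use 2 + 1 + 1 = 4 degrees of freedom. The t critical value moves from 1.64805 (478 df) to 1.64807 (474 df). In simulation the interval widens by about 0.01% with 480 evaluable and by about 0.3% with about 300.

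**3. Gain if they explain something.** The half-width is multiplied by sqrt(1 − R²). The lowest observed ratio that passes is 0.80 × exp(t × 0.5545 × sqrt(2/n) × sqrt(1 − R²)). At n = 240 and R² = 0 this is 0.80 × exp(0.0834) = 0.870.

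| Assumed R² | CI narrower by | Lowest passing ratio, 240 per arm | Lowest passing ratio, 150 per arm |
|---|---|---|---|
| 0% | 0% | 0.870 | 0.889 |
| 10% | 5% | 0.866 | 0.884 |
| 20% | 11% | 0.862 | 0.879 |
| 30% | 16% | 0.858 | 0.874 |

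**4. Validity of the unadjusted test.** After stratified blocks its effective critical value is about 1.645/sqrt(1 − R²). That is 1.734, 1.839 and 1.966 at R² of 10, 20 and 30%, with upper tails of 0.041, 0.033 and 0.025.

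A simulation at a true ratio of 0.80 agrees. It assumed blocks of 4, and stratum shares of 30/45/25% for weight, 60/40% for lines and 60/40% for type, with 25,000 trials per setting (Monte Carlo SE 0.0014). One-sided type I error, nominal 0.05:

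| R² | 480 evaluable: unadjusted / adjusted | About 300 evaluable at random: unadjusted / adjusted |
|---|---|---|
| 0% | 0.052 / 0.052 | 0.050 / 0.049 |
| 10% | 0.042 / 0.049 | 0.047 / 0.050 |
| 20% | 0.033 / 0.051 | not run |
| 30% | 0.026 / 0.052 | 0.035 / 0.051 |

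**5. When power would change.** At the planned ratio of 1 there is almost nothing to gain at 240 per arm. At a true ratio of 0.90, which is not the planning value, simulated power (8,000 trials per setting) is:

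| R² | 240 per arm: unadjusted / adjusted | 150 per arm: unadjusted / adjusted |
|---|---|---|
| 0% | 75% / 75% | 58% / 58% |
| 10% | 77% / 79% | 58% / 62% |
| 30% | 79% / 87% | 59% / 71% |

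**The case against.** The strongest reply is that nothing is wrong. Planned power is 99.7%, the unadjusted test errs on the safe side, and in a non-inferiority trial a conservative test means fewer false claims. A material gain needs conditions that the documents do not point to:
- **True ratio.** The plan assumes 1. Protocol 3.2 reports subcutaneous troughs comparable to or higher than intravenous ones.
- **R².** No value is given. Protocol 3.2 predicts similar exposure across weight quartiles, so weight may explain little. Nothing links prior lines or myeloma type to trough. The prognostic groups in Protocol 3.2 concern balance at randomisation, not pharmacokinetics.
- **Evaluable numbers.** 150 per arm is an assumption, and even there power at a ratio of 1 is 96.7%.

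All of this stands. It limits the size of the gain but does not remove the asymmetry: negligible cost if the factors are irrelevant, a tighter interval if they are not.

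It may also be said that unstratified ORR is accepted because the trial was sized on that test, and that Ctrough was likewise sized without covariates. The difference is that Protocol 11.3 names the ORR test, whereas no Ctrough model is named anywhere. Adjusting on the log scale still yields a geometric mean ratio judged against the same margin.

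Three stronger readings are tempting, and the documents support none of them:
- *The plan excludes the factors.* SAP 7.1.1 is silent on the model. The unadjusted reading is the natural one, but it is not stated.
- *The Ctrough test is invalid or underpowered.* Steps 1 and 4 show otherwise.
- *The ORR test should be stratified too.* The unstratified Farrington-Manning test is what the trial was sized on, and it estimates the relative risk in the SAP 5.2.2 estimand. ORR by each of the three factors is already pre-specified in SAP 2.10, Table 1, with a forest plot in SAP 5.5. That is not a pooled stratified estimate, but adding one would be expected to change no conclusion.

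**Conclusion.** The point holds as a free improvement. The co-primary Ctrough analysis should name its model, and the sensible model uses the factors on which the trial is randomised, as the four hierarchy endpoints already do. It is a matter of efficiency and clear specification, not of validity.

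The size is modest: a 90% CI narrower by 5 to 16% for an assumed R² of 10 to 30%, and a passing threshold lower by 0.004 to 0.012 at 240 per arm (0.005 to 0.015 at an assumed 150). If R² is zero there is no gain and no meaningful loss. The stated power above 95% is met without adjustment as long as about 134 per arm are evaluable, at the planned ratio and CV. The R² values, the 150 per arm, the block size and the stratum shares are assumptions, not figures from the documents.

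**What to change.** In SAP 7.1.1, state that log maximum Ctrough will be fitted in a linear model with treatment and the three randomisation factors as main effects, using the values recorded at randomisation. The treatment difference and its 90% CI are back-transformed to the geometric mean ratio. Keep the 80% rule and the PK-evaluable set, and report the unadjusted ratio alongside. Main effects need no pooling of sparse cells. The model should be fixed before concentrations are compared by arm.

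The cost is a sentence and a few lines of code. No new data are needed, and the margin, alpha, sample size, success rule and ORR analysis stay as they are. Protocol 11 leaves specific details to the SAP, and the general description in Protocol 11.5 would remain true, so it need not be amended for this alone.

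Two additions are optional only:
- A descriptive Ctrough ratio by weight stratum. With an assumed 60 per arm in a stratum, the 90% CI runs from the estimate divided by 1.18 to the estimate times 1.18, too wide for a test against 80%.
- A Mantel-Haenszel relative risk for ORR over the randomisation strata, as a sensitivity analysis.

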### 7.1.2. Other Pharmacokinetic Parameters

The following pharmacokinetic parameters will also be summarized on the pharmacokinetics analysis set:

- Minimum observed concentration ( $C_{\text{min}}$ ): defined as the concentration observed immediately before dose administration;
- Maximum observed concentration ( $C_{\text{max}}$ ): defined as the concentration observed after the end of dose administration.

The  $C_{\text{min}}$  and  $C_{\text{max}}$  will be determined based on assigned collection timepoint. Descriptive statistics will be used to summarize daratumumab serum concentrations at each sampling time point specified in protocol. Plot of mean ( $\pm$ standard deviation) daratumumab serum peak and trough concentrations over time will be provided.

A scatter plot of daratumumab serum concentration over time will also be provided.

If sufficient data are available, other pharmacokinetic parameters may be calculated and analyzed.

